## **8 Patient selection criteria**

### **8.1 Inclusion criteria**

1. Morphologically (pathology or cytology) verified, previously untreated SCCs of the oral cavity, oropharynx, uterine cervix, esophagus, anal canal or lung.
2. The patient should be planned for treatment with radiotherapy alone or in combination with concomitant medical therapy
3. The tumour shall be radiologically and/or visually identifiable and accessible for biopsy without the need for general anaesthesia or other major interventions
4. The patient must be at least 18 years of age, able to understand the given information and, leave a written informed consent to participate

### **8.2 Exclusion criteria**

1. The patient is unwilling to participate in the study
2. Patients with adjuvant post-operative radiotherapy (i.e. no visible remaining tumour)
3. Pregnancy or lactation
4. Contraindications to investigations with MRI, gadolinium contrast or PET-tracers
5. Patients with an estimated GFR <60 ml/min/1.73m^2.
6. Severe co-morbidities that are judged to significantly compromise survival in a two-years perspective.

## **9 Study procedure**

### **9.1 Study entry**

#### **9.1.1 Mandatory investigations**

1. Adequate clinical assessment with a TNM classification and histology/FNAC (showing squamous cell carcinoma).
2. Body weight and height
3. ECOG Performance status
4. P-Creatinine

5. Tumour biopsy and blood sampling in patients participating in the exploratory part of the study.
6. Registration form including informed consent
7. The disease specific module of the EORTC QLQ-C30 for reporting late RT effects should be offered for the patient to fill out and forward to the data centre in a pre-stamped envelope. With the exception of sites where no such module is available.

Investigations number 1-4 are clinical routine investigations, and are thus not regarded as study specific procedures.

### **9.1.2 Instructions regarding women of childbearing potential**

Pregnancy must be excluded before a fertile woman can be included in the study.

## **9.2 Evaluation during treatment**

Concomitant anticancer medication should be recorded with substance, dose and time for administration in the CRF.

## **9.3 Evaluation after completion of treatment**

At two months after completion of therapy an assessment of tumour control and morbidity must be made. Tumour control is assessed by clinical examination together with endoscopy, palpation, control biopsies and appropriate imaging as judged indicated by the responsible physician.

## **9.4 Surgery**

If surgery is performed, this must be recorded.

## **9.5 Follow-up**

- Patients should be seen every three months for two years after completion of radiotherapy and a full clinical assessment should be made.
- One year after end of radiotherapy, the patient will be asked to fill out the disease specific module of the EORTC QLQ-C30 for reporting late RT effects. The questionnaire will be distributed to the patient at the time of inclusion in the study and posted to living patients after one year. One year after completion of radiotherapy the questionnaire will be posted to living patients for self-assessment of late radiotherapy side effects. If not answered, one reminder will be distributed.
- After two years, evaluation of locoregional control should be made every 6 months up to 5 years. At five years, a last follow-up is recommended at the treatment centre with the aim at evaluating late side effects. Any additional follow-up beyond 5 years is not included in the study protocol, each physician decides on further follow-up.

Patients should be monitored for local recurrence and if symptoms arise that are suspicious of distant metastases appropriate investigations must be carried out to confirm or exclude their presence. Also, **if a locoregional recurrence is found, a CT/MR for documentation is mandatory and screening for distant metastases should be performed.** If distant metastases develop but there is no evidence of local recurrence within the irradiated volume, effort should be made to continue to monitor the primary site. **In all cases histological confirmation should be performed.**

## 9.6 End of treatment or follow-up

Follow-up by the protocol ends when any of the events below occurs:

- If 5 years of follow-up is reached
- If residual tumour or a locoregional recurrence is diagnosed that cannot be treated with curative intent. Survival will then be followed by the Swedish population registry
- In cases of other serious medical conditions, follow-up ends as judged by the investigator. Survival will then be followed by the Swedish population registry
- If the patient dies before 5 years' follow up
- Withdrawal of consent

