**Statistical methods**

To find potentially relevant patterns of response in the large amount of data for each patient, chemometric methods will be applied

To estimate the degree of agreement between predicted and observed response the Cohen's Kappa will be used.

Criteria for evaluation	Patients who have undergone per protocol imaging sessions before and during therapy
Planned sample size	412 patients
Analysis plan	The primary endpoint will be analysed when median follow up is two years.
Duration of the study	Three to four years inclusion, five year follow-up after inclusion of the last patient.

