## **4.2 End points**

### **4.2.1 Primary end point**

- Loco-regional control 2 years after completion of radiotherapy

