For personalised therapy purposes a correct classification in 90 % of cases is desired. We assume that the proportions of responding patients are either distributed similarly (50 %/50 %) or that only 20 % are responders.  $H_0: k = k_0$ ,  $H_1: k = k_1$ ,  $k_1 > k_0$ . Assuming  $k_0 = 0.4$  (which is considered to indicate a poor agreement) and  $k_1 = 0.7$  (which is considered to indicate a good agreement) and if the probability of correct rejection of  $H_0$  is set to 90 % the number of patients needed is 63 or 80 depending on response rates (50 % or 20 %). Thus, a number of patients of about 70 for each study group should be optimal to answer the study questions. In addition to the 70 patients of each group, the data from 30 patients from the head and neck cancers and lung cancers will be used for hypothesis generation. Their data will not be re-used for validation. From previous experience, a proportion of patients will for medical or other reasons not contribute with the second set of data. It is assumed that 20% of patients will have incomplete data sets. Thus, the number of included patients in each group will be aimed at 100. Additionally, the 30 first patients will be part of a pilot study and not analysed further for the study end-points. The total number of patients needed for the study is estimated to 412 during the three years of accrual. However, each group will be closed earlier for further inclusion if 100 evaluable patients are reached. Image and bio-marker analyses will be performed only on those with complete data sets from imaging sessions.

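### Section 9.6 lets loco-regional status, the primary endpoint, go uncollected in living patients before 2 years, and the sample size makes no allowance for unknown status

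*Protocol*

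**What the plan says.** Protocol Section 4.2.1 sets the primary endpoint as a status at a fixed time: "Loco-regional control 2 years after completion of radiotherapy". The Synopsis, under Statistical methods, gives the measure: "To estimate the degree of agreement between predicted and observed response the Cohen's Kappa will be used". Section 12.1 sizes the study on a test of kappa 0.4 against 0.7 with 90% power. It arrives at 63 patients if half respond and 80 if one in five respond, and concludes: "Thus, a number of patients of about 70 for each study group should be optimal to answer the study questions". A further 30 patients are set aside for hypothesis generation, of whom it says: "Their data will not be re-used for validation".

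The allowance for loss follows a sentence about patients who do not provide the second set of data: "It is assumed that 20% of patients will have incomplete data sets". Section 12.1 then limits image and biomarker analyses to patients with complete imaging data. It sets no condition on the 2-year outcome.

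Section 9.6 lists the events that end protocol follow-up. One is discretionary: "In cases of other serious medical conditions, follow-up ends as judged by the investigator". From then on only survival is followed, through the population registry. Section 9.5 takes a different line for patients who develop distant metastases without local recurrence: "effort should be made to continue to monitor the primary site".

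**The concern.** A 2-year control status has to be observed. A population registry supplies the date of death, not the state of the primary tumour or the nodes. A patient stopped under the discretionary item of 9.6 at, say, 10 months may be alive at 2 years with no recorded loco-regional outcome, and no one will have departed from the protocol.

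Sections 9.5 and 9.6 can also apply to the same patient. Someone with distant metastases and no local recurrence may be judged to have another serious medical condition, and nothing says which section prevails. Section 12.2 promises every effort to collect survival data but makes no such statement for loco-regional status.

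Two things are at stake: how many patients can enter the primary agreement analysis, and whether those who can are still representative. An analysis plan can choose how to handle missing status, but it cannot recover status that was never collected.

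**Working it through.** **1. What the total contains.** Section 12.1 does not show the sum behind 412. Three groups of 100 (70 for validation plus 30 for hypothesis generation) and 30 pilot patients, inflated for 20% loss, give (3 × 100 + 30) / 0.8 = 412.5. On this arithmetic the whole 20% goes to missing second-session data, and nothing is left for unknown 2-year status.

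**2. The protocol's 63 and 80.** Inputs from 12.1: kappa 0.4 and 0.7, one-sided alternative, 90% power, 50% or 20% responders. Alpha is not stated; one-sided 5% is assumed here. With equal margins and responder share p, the large-sample variance of kappa is Q/n, where

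Q(k, p) = (1 − k) × [(1 − k)(1 − 2k) + k(2 − k) / (2p(1 − p))].

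- p = 0.5: Q(0.4) = 0.84 and Q(0.7) = 0.51.
- p = 0.2: Q(0.4) = 1.272 and Q(0.7) = 0.817.
- n = [(1.645 √Q(0.4) + 1.282 √Q(0.7)) / 0.3]², which gives 66 and 101.

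These are not 63 and 80, and no variant tried (other variances, a goodness-of-fit approach, other alpha and power) gives both. The formula reaches 63 with a one-sided alpha of 0.055 and 80 with 0.088. The main reading below is therefore scaled to the protocol's own figures (90% power at 63 and at 80), with the unscaled formula beside it.

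**3. Effect of unknown status if those patients drop out of the table.** The documents give no loss rate, so 0 to 30% is an assumed range. Power = Φ[(0.3 √n − z √Q(0.4)) / √Q(0.7)]. For the scaled columns z is set so that power is 90% at 63 (z = 1.60) or at 80 (z = 1.35). For the others z = 1.645.

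| Status unknown | n of 70 left | 50% resp., scaled | 20% resp., scaled | 50% resp., one-sided 5% | 20% resp., one-sided 5% |
|---|---|---|---|---|---|
| 0% | 70 | 93% | 86% | 92% | 77% |
| 10% | 63 | 90% | 83% | 89% | 72% |
| 20% | 56 | 86% | 79% | 85% | 67% |
| 30% | 49 | 81% | 74% | 80% | 61% |

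At 50% responders the margin is 70 − 63 = 7 patients, or 7/70 = 10%. At 20% responders power is below 90% in the first row, because 70 is less than 80. That shortfall comes from the choice of 70, not from 9.6; only the further fall down the column comes from status loss.

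**4. Direction of bias if loss depends on prognosis.** Take 50% responders and a true kappa of 0.70: 42.5% in each concordant cell and 7.5% in each discordant cell. Remove 30% of selected cells and recompute kappa = (observed − expected) / (1 − expected).

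- 30% of all observed failures lost: kappa 0.69.
- 30% of those both predicted and observed to fail lost: kappa 0.65. Observed agreement is 0.7225/0.8725 = 0.828 and expected agreement is 0.511.
- 30% of the discordant patients lost: kappa 0.78. Observed agreement is 0.85/0.955 = 0.890 and expected agreement is 0.5.

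Agreement can move down or up, depending on who is lost.

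**The case against.** The strongest reply is that the loss may be small. Section 8.2 excludes co-morbidity expected to compromise two-year survival. Section 9.5 has visits every three months for two years, so failures before a stop are usually already known. Stopping for residual tumour or incurable recurrence loses nothing, because the failure has been recorded. Section 9.6 ends only follow-up by the protocol; the Synopsis has patients followed by clinical routine for at least two years, and Section 13.1 names the medical record as a source. All of this stands and reduces the loss. It does not close the gap: the exclusion concerns illness known at entry, and nothing requires anyone to consult the record after a discretionary stop.

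A reader might infer that the stated 90% power is not delivered. The documents do not support that. They give no loss rate, and at 50% responders 10% loss leaves exactly the protocol's 63. Section 12.1 also provides for analysis of all groups together: 3 × 70 = 210, and 30% loss leaves 147, where the one-sided 5% formula gives power above 97% at either responder share. The size issue therefore concerns the separate analyses, chiefly lung and head and neck.

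A reader might also infer that the loss is known to be informative. That is plausible, since serious illness can be related to tumour response, but it is not shown and step 4 gives no fixed direction. A still stronger reading codes unknown status as controlled, which at 50% responders would take kappa from 0.70 to 0.63, 0.56 or 0.49 if 10, 20 or 30% of true failures were missed. The protocol states no such coding rule, and the calculation assumes that none of those failures was seen before the stop.

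Two further points are fair. The kappa text speaks of response and outcome and does not name 2-year control, so linking it to the primary endpoint is an inference, though this is the only sizing given. And death before 2 years is a competing event that no follow-up rule removes; its handling in the agreement table may properly sit in the analysis plan.

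**Conclusion.** The concern holds in a limited form. Section 9.6 allows the primary endpoint to go uncollected, at discretion, in living patients, and it sits uneasily with 9.5. The 20% in 12.1 is for missing second-session data, and neither 70 per group nor 412 in total allows for unknown 2-year status.

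The effect on power depends on a loss rate that the documents do not give. At 50% responders the protocol's own figures tolerate about 10% loss before power drops below 90%. At 20% responders the group size is short before any status is lost. These figures assume that patients without status are dropped, that the kappa test applies to 2-year control, and that scaling to the protocol's 63 and 80 is a fair reading where alpha is unstated. Bias is possible in either direction and cannot be quantified from the documents.

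**What to change.** In Section 9.6, state that the discretionary event ends study visits only, and that loco-regional status continues to be taken from the medical record until 2 years after completion of radiotherapy, unless consent is withdrawn or the patient dies. Reconcile this wording with Section 9.5, so that a patient with distant metastases who also meets the 9.6 item falls under one rule. This concerns data capture only and changes no treatment.

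In Section 12.1, restate the power for the number of patients expected to have a known 2-year status, show the assumed loss rate, and keep it distinct from the 20% for missing second-session data. The trial need not be enlarged; the purpose is that the stated power matches the patients who can be analysed.

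The cost is some record review for what should be few patients, an amendment to two sections, and a slightly less favourable stated power.

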## 10 Radiotherapy

Radiotherapy will be performed according to clinical routines of each participating centre. The patients may be treated with X-rays, electrons or protons.

### 10.1 Patient position and fixation

The patient should be treated in supine position, adequately positioned and fixated according to the routines at each treatment centre.

### 10.2 Patient radiotherapy data acquisition

Full 3-D treatment plans together with data from the oncology information system will be stored in the local research database at each treatment centre. The use of the nationally agreed research database for radiotherapy (MIQA) is recommended. The collection of data that will be sent to the coordinator of RT-data will be anonymised and assigned the patient's number in the study when the selection of relevant data is analysed. A treatment planning imaging (slice thickness  $\leq 3\text{mm}$ ) should be performed with the patient in treatment position, adequately fixated. Optionally, a co-registered MRI- or PET-scan should also be performed as aid for tumour delineation.

## 11 Biobank

As primary biobank, Biobank Norr in Umeå, will be used. Until analysis samples will be kept in the local bio-banks at each hospital.

## 12 Statistical plan

### 12.1 Sample size determination

From the expected number of eligible patients with each diagnose, three separate study groups are identified

1. Lung cancer
2. Head and neck cancer
3. Cervix, esofagus and anal carcinoma

The first two subgroups will be analysed separately as well as aggregated with all other groups. In group no 3 the number of patients with each diagnosis is expected to be too low to make valid statements for each entity. This group will therefore mainly be analysed together with all cases.

The overall aim of the study is to identify and validate parameters predictive to outcome of treatment. To estimate the degree of agreement, the Cohen's Kappa is commonly used. It is defined as the proportion on the main diagonal that exceeds the expected number if a random classification is performed. It is normalised to fit the interval (0,1) where 0 is a random classification and 1 is a 100% correct classification.

For personalised therapy purposes a correct classification in 90 % of cases is desired. We assume that the proportions of responding patients are either distributed similarly (50 %/50 %) or that only 20 % are responders.  $H_0: k = k_0$ ,  $H_1: k = k_1$ ,  $k_1 > k_0$ . Assuming  $k_0 = 0.4$  (which is considered to indicate a poor agreement) and  $k_1 = 0.7$  (which is considered to indicate a good agreement) and if the probability of correct rejection of  $H_0$  is set to 90 % the number of patients needed is 63 or 80 depending on response rates (50 % or 20 %). Thus, a number of patients of about 70 for each study group should be optimal to answer the study questions. In addition to the 70 patients of each group, the data from 30 patients from the head and neck cancers and lung cancers will be used for hypothesis generation. Their data will not be re-used for validation. From previous experience, a proportion of patients will for medical or other reasons not contribute with the second set of data. It is assumed that 20% of patients will have incomplete data sets. Thus, the number of included patients in each group will be aimed at 100. Additionally, the 30 first patients will be part of a pilot study and not analysed further for the study end-points. The total number of patients needed for the study is estimated to 412 during the three years of accrual. However, each group will be closed earlier for further inclusion if 100 evaluable patients are reached. Image and bio-marker analyses will be performed only on those with complete data sets from imaging sessions.

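### The sample sizes 63 and 80 in Protocol 12.1 do not follow together from the stated inputs if the predicted responder share equals the response rate; on that reading 80 is too few

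*Protocol*

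**What the plan says.** Section 12.1 of the Protocol sizes each study group by a test of Cohen's kappa between predicted and observed response. The null value is 0.4, the alternative is 0.7, and the hypothesis is directional (k1 > k0). The response rate takes two values: "We assume that the proportions of responding patients are either distributed similarly (50 %/50 %) or that only 20 % are responders". With the probability of correctly rejecting the null at 90%, "the number of patients needed is 63 or 80 depending on response rates (50 % or 20" %). From this the section concludes that "a number of patients of about 70 for each study group should be optimal to answer the study questions".

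On the choice of statistic the section says only "To estimate the degree of agreement, the Cohen's Kappa is commonly used", followed by a verbal definition. It states no significance level and no sample-size formula. It gives one rate per scenario, the share who respond, and not the share the predictor classifies as responders. The section also says that the lung and head and neck groups will be analysed separately as well as pooled.

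**The concern.** The two sizes differ only in the response rate, so their ratio can be checked even though alpha is missing. The stated ratio is 80/63 = 1.27. Kappa is estimated much less precisely at a 20% rate than at 50%, and the usual formulas give a larger ratio than this.

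The 20% case is the harder of the two scenarios on which the groups are sized. If its figure is too low, a predictor with a true kappa of 0.7 would fail validation in a single group more often than the 10% the text implies, and a negative result could be over-read as evidence that the predictor does not work. Validation of early predictors is one of the specific aims (section 4.1.2).

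**Working it through.** **Inputs from section 12.1:** k0 = 0.4, k1 = 0.7, power 90% (z = 1.2816), response rate p = 0.5 or 0.2. **Assumptions:** alpha is not stated, so it is varied and also solved for; the predicted share equals p (equal margins) until step 5.

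**1. Formula.** With equal margins the large-sample variance of kappa is Q/n, where

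Q(k,p) = (1−k)[(1−k)(1−2k) + k(2−k)/(2p(1−p))]

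n = [(z_alpha·√Q0 + z_power·√Q1)/(k1−k0)]²

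| p | Q0 (k = 0.4) | Q1 (k = 0.7) |
|---|---|---|
| 0.5 | 0.840 | 0.510 |
| 0.2 | 1.272 | 0.817 |

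**2. Attempt to reproduce 63 and 80.**

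| One-sided alpha | n at 50% | n at 20% |
|---|---|---|
| 10% | 49 | 76 |
| 5% | 65.2, so 66 | 100.9, so 101 |
| 2.5% | 81.7, so 82 | 126.1, so 127 |

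No row gives the stated pair.

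**3. Why alpha cannot repair it.** The ratio of the two sizes must lie between Q0(0.2)/Q0(0.5) = 1.272/0.840 = 1.51 and Q1(0.2)/Q1(0.5) = 0.817/0.510 = 1.60, whatever positive z_alpha is used. The goodness-of-fit method for kappa gives 79.9 and 116.6 at one-sided 5%, a ratio of 1.46 that does not depend on alpha. The stated ratio, 1.27, is outside all of these.

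If alpha is chosen so that n = 63 at 50% responders:

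| Method | One-sided alpha | n at 20% |
|---|---|---|
| Goodness of fit | – | 63 × 1.459 = 91.9 |
| Null variance only | 0.094 | 95.4 |
| Both variances | 0.055 | 97.5 |
| Alternative variance only | 0.020 | 100.9 |

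Conversely, if 80 were right at 20%, the 50% figure would be about 80/1.60 = 50 to 80/1.46 = 55, not 63.

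**4. Power with equal margins.** Power = Φ[(0.3·√n − z_alpha·√Q0)/√Q1].

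| n | Responders | One-sided 5% | One-sided 2.5% |
|---|---|---|---|
| 63 | 50% | 89% | 79% |
| 70 | 50% | 92% | 84% |
| 80 | 20% | 82% | 70% |
| 70 | 20% | 77% | 63% |

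Simulation at one-sided 5% gave 82 to 84% for 80 patients at 20% responders, depending on how the test is calibrated.

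**5. Unequal margins.** The general kappa variance, both variances used, one-sided 5%, 90% power:

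| True share | Predicted share | n |
|---|---|---|
| 50% | 40% or 60% | 62.6, so 63 |
| 20% | 30% | 80.7, so 81 |
| 20% | 25% | 91.1 |
| 20% | 15% | 109.2 |

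With margins of 20% and 30%, 80 patients give 89.7% power and 70 give 85%. With 20% true and 10% predicted, a kappa of 0.7 cannot be reached: it would require a negative cell.

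**The case against.** The strongest counter-argument is step 5. Kappa depends on two margins and the protocol states one. If the predictor's share differs from the true rate by 10 points, an ordinary one-sided 5% test gives 63 and 81 (and 80 at a predicted share of about 30.4%). Equal margins do not produce 63 at a conventional one-sided 5% or 2.5% under the two-variance formula, so equal margins may not be the model that was used. A reader might infer from the mismatch that 80 is a plain miscalculation, or that 63 and 80 are incompatible under every method. The protocol does not support that: it leaves out the inputs that would decide the matter.

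This part stands, and it makes the finding conditional. It does not remove it, for three reasons:

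- The unequal shares were found by searching for a fit. Nothing in the protocol mentions them.
- In the 20% scenario they work in one direction only: the predictor must over-call responders by half. A 5-point over-call still needs about 91 patients, and under-calling raises the number.
- They sit poorly with the section's own wish to classify nine patients in ten correctly. With margins of 20% and 30%, agreement at kappa 0.7 is 88.6%, and no classifier with those margins can exceed 1 − 0.10 = 90%. With equal margins at 20%, kappa 0.7 corresponds to 90.4% agreement. This is only a hint, since in the 50% scenario kappa 0.7 means 85% agreement.

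It is also fair to say that a formula could be left to a statistical analysis plan, that no design number rests on 80 alone because 70 was adopted, that pooled analyses are planned too, and that treatment is unaffected by the results. These points limit the severity. They do not make the printed figures follow from the printed inputs.

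**Conclusion.** The concern holds conditionally. If the share predicted to respond equals the stated response rate, 63 and 80 do not both follow from kappa 0.4 against 0.7 with 90% power, for any alpha and under any of the variance or goodness-of-fit methods tried. Anchored at 63, the 20% case needs about 92 to 101 patients. At one-sided 5%, 80 patients then give about 82% power; the adopted 70 give about 77%, so a predictor with a true kappa of 0.7 would be missed about 23% of the time rather than 10%. At 50% responders, 70 patients give about 92%, so that scenario is adequately served on this alpha.

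Under the most favourable unequal margins found, the stated pair is essentially recovered, but 70 patients still give only about 85% at 20% responders. On neither reading does the adopted size deliver 90% in that scenario at one-sided 5%.

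That 70 lies below the protocol's own 80 is a separate matter. With equal margins, raising the group size to 80 would not restore 90%. Nor does the finding show that the study must recruit more patients; it concerns the power that is claimed.

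This should be fixed. Confidence is moderate, because alpha, formula and the second margin are all unstated.

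**What to change.** In Protocol 12.1:

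1. State the significance level and sidedness, the sample-size formula, and both margins in each scenario: the true and the predicted responder share.
2. Recompute the two sizes from those inputs. With equal margins, one-sided 5% and the two-variance formula they are 66 at 50% responders and 101 at 20%. If unequal margins were intended, give them and the reason for them.
3. Replace the implied 90% with the power that 70 patients per group give in each scenario: about 92% and 77% with equal margins at one-sided 5%.

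The cost is a sentence or two of text and a less favourable stated power at 20% responders. Accrual need not change.

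### The 70 patients adopted per group fall short of the protocol's own 80 for 20% responders, and the group target, the total of 412 and the hypothesis-generation rule leave the validation size open

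*Protocol*

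**What the plan says.** All of this is in the protocol.

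- **Size for 90% power (12.1).** The test sets kappa 0.4 against a larger value, 0.7. On the size required, the text says "the number of patients needed is 63 or 80 depending on response rates (50 % or 20", both figures being percentages of responders. It then adopts one figure: "Thus, a number of patients of about 70 for each study group should be optimal to answer the study questions".
- **Separate analyses (12.1).** Lung cancer and head and neck cancer are each to be analysed on their own as well as pooled. The third group (cervix, oesophagus, anal canal) is mainly analysed in the pool.
- **Hypothesis generation (12.1).** On top of the 70, "the data from 30 patients from the head and neck cancers and lung cancers will be used for hypothesis generation". These data are barred from validation.
- **Loss (12.1).** The allowance for missing second assessments is a fifth: "It is assumed that 20% of patients will have incomplete data sets".
- **Target (12.1).** The figure drawn from this is stated in patients entered: "Thus, the number of included patients in each group will be aimed at 100".
- **Total (12.1).** Thirty pilot patients come on top and do not count towards the end-points. The overall figure follows without a derivation: "The total number of patients needed for the study is estimated to 412 during the three years of accrual".
- **Closing rule (12.1).** Early closure is tied to a different unit from the target: "However, each group will be closed earlier for further inclusion if 100 evaluable patients are reached".
- **Who is analysed (12.1).** The analysis set is limited to complete cases: "Image and bio-marker analyses will be performed only on those with complete data sets from imaging sessions". The synopsis likewise counts only patients imaged both before and during therapy.
- **Hypothesis generation again (12.4).** A random one in four patients forms this group, with no limit by site, and is again kept out of validation. Section 12.2 mentions a randomised fraction held back for validation and does not give its size.

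**The concern.** The study's purpose is to validate predictors, so the number that matters is the count of complete patients left for validation in each group that is analysed alone. Section 12.1 gives 80 as the requirement in one of its two scenarios and adopts 70 without saying what that costs. It then states the target in included patients and the closing rule in evaluable patients, and gives a total with no derivation. Sections 12.1 and 12.4 remove different patients for hypothesis generation.

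The choice of unit decides whether a group stops with about 80 or about 100 complete patients. The hypothesis-generation rule decides whether 70, 75 or 85 of 100 evaluable patients remain for validation, which is below or above the plan's own 80.

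**Working it through.** **Inputs from 12.1:** k0 = 0.4, k1 = 0.7, one-directional alternative, 90% power, responders 50% or 20%, 63 or 80 patients, 70 adopted, 20% incomplete, 30 pilot patients, three groups, total 412. **Assumed:** one-sided alpha of 5% or 2.5%, because none is printed.

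**1. The plan's own 63 and 80.** With the large-sample variance of kappa, n = [(z(1-alpha)·√Q0 + z(0.90)·√Q1)/(k1 - k0)]². When predicted and observed responder shares both equal p, Q = (1-k)[(1-k)(1-2k) + k(2-k)/(2p(1-p))].

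- p = 0.5: Q0 = 0.84, Q1 = 0.51. At one-sided 5%, n = [(1.645×0.917 + 1.282×0.714)/0.3]² = 65.2.
- p = 0.2: Q0 = 1.272, Q1 = 0.817. At one-sided 5%, n = [(1.645×1.128 + 1.282×0.904)/0.3]² = 100.9.
- With unequal shares (50% and 40%; 20% and 30%), the general form of the variance gives 62.6 and 80.7, close to the printed figures.

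The predicted share is not stated, so 63 and 80 cannot be confirmed or rejected. They are taken below as giving exactly 90%.

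**2. Power at 70.** Scaling from N patients at 90%: power = Φ[(z(1-alpha) + 1.282)·√(n/N) - z(1-alpha)].

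- 20% responders, N = 80: √(70/80) = 0.935. One-sided 5%: 2.926×0.935 - 1.645 = 1.09, power 86.3%. One-sided 2.5%: 3.242×0.935 - 1.960 = 1.07, power 85.8%. Using Q0 and Q1, rescaled so that 80 gives 90%, the results are 85.7% and 85.1%. Range 85.1-86.3%.
- 50% responders, N = 63: √(70/63) = 1.054. One-sided 5%: 2.926×1.054 - 1.645 = 1.44, power 92.5%. Range over the same variants 92.5-93.1%.
- Pooled, 3×70 = 210 validation patients: above 99% in either scenario.

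**3. Target, closing rule and total.** 100 included × 0.8 = 80 complete, against a closing rule of 100 evaluable.

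| Sum | Total |
|---|---|
| 3×100 included + 30 pilot | 330 |
| the same + 30 for hypothesis generation | 360 |
| the same + 2×30 for hypothesis generation | 390 |
| A: (3×100 evaluable + 30 pilot)/0.8 | 412.5 |
| B: 3×100 included + (2×30 hypothesis generation + 30 pilot)/0.8 = 300 + 75 + 37.5 | 412.5 |

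Under A, a group that gives 30 of its 100 evaluable patients to hypothesis generation keeps 70 for validation. Under B, 80 complete patients remain for validation, and lung and head and neck each have 80 + 30 = 110 complete. If such a group closes at 100 evaluable, 100 - 30 = 70 remain.

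**4. Hypothesis-generation rule, with 100 evaluable in a group.**

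| Rule | Left for validation | Power at 20% responders (80 = 90%) |
|---|---|---|
| 30 per group (12.1) | 70 | 85-86% |
| one in four (12.4) | 75 | 88% |
| 30 shared by two groups, 15 each (12.1) | 85 | about 92% |

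**The case against.** **The 70 is a visible compromise.** Both 63 and 80 are printed, their midpoint is 71.5, and the text does not claim 90% power at 70 in the 20% scenario. This stands in part: it is not an arithmetic error. But calling 70 optimal hides a loss of 4 to 5 points in one of the two scenarios.

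**The size of the loss is conditional.** Alpha is not printed and the 80 is not reproduced with equal shares. This stands, and the 85-86% is stated only on the plan's own 80. A reader might go further and infer that 80 is itself too low, since equal 20% shares need about 101 patients and leave about 77% at 70 (one-sided 5%). The protocol does not give the predicted share, so it does not support that step.

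**A reader might infer that 100 included cannot be squared with 412, or that the closing rule can never take effect.** Neither follows. Derivation B starts from 100 included, reaches 412.5 and leaves 110 complete patients in lung and in head and neck, so early closure could occur. It also fits the statement that hypothesis-generation patients come on top of the 70. Both A and B inflate the pilot patients for loss, and nothing in the text chooses between them.

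**A reader might infer that only 50 patients remain** (80 complete less 30). That places the hypothesis-generation patients inside the 100 included, whereas 12.1 describes them as additional to the 70.

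**The two hypothesis-generation rules are close in number.** One in four of 125 included is about 31, near 30 per group. This stands if 30 per group is meant. The rules still differ in sites covered and in fixed number against fraction, and the 30 may be shared. The fraction in 12.2 is set aside for validation, which agrees with 12.4, so it is not a third rule.

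**Conclusion.** The point holds as an undisclosed loss of power in one scenario and a validation size that the protocol does not fix. On the plan's own 63 and 80, with one-sided alpha of 5% or 2.5% assumed, 70 validation patients give about 92-93% power at 50% responders and 85-86% at 20%. The shortfall applies to lung and to head and neck analysed alone. The pooled validation is not at risk.

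Whether the shortfall arises depends on matters left open. Under A with 30 per group, 70 remain. Under B, 80 remain and there is no shortfall unless a group closes at 100 evaluable. With 30 shared between two groups of 100 evaluable, 85 remain. The total of 412 is not shown to be wrong; its derivation is missing, and the included and evaluable figures beside it are in different units.

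**What to change.** 1. In 12.1, state alpha and the power of the adopted validation size for each responder scenario. For 70 patients, on the plan's own 63 and 80, this is about 92-93% at 50% responders and 85-86% at 20%.
2. Have the sponsor confirm which derivation gives 412 and print it. Express the per-group target and the closing rule in the same unit, complete imaging data, with the matching number included beside it.
3. Use one hypothesis-generation rule in 12.1 and 12.4, and make the fraction in 12.2 match. State the resulting validation size for lung and for head and neck. With 100 evaluable, this is 70 (30 per group), 75 (one in four) or 85 (30 shared).

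The cost is protocol wording, with no extra patients. The downside is that a power of about 85% becomes visible for the 20% scenario if 70 is kept.
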